#### Intervention Group

Patients in the intervention group will receive text messages focused on smoking cessation and pregnancy. An initial text message will be sent 2-3 days prior to their quit date, with subsequent message being sent, 1 day prior to the quit date, on their quit and continued in a de-escalating fashion until they deliver. Patients will also receive text messages when they need to replenish their smoking cessation patches. Patients will be contacted through Google Voice which is a Google system requiring a secure login and password. The user name for this account is [contact] and the phone number which will be contacting the patient is [contact].

#### Follow-up phone calls and visits for Intervention and Control Groups

Usual follow-up includes a telephone call to the patient within 3 days of the quit date then weekly for 2 weeks afterwards. Each phone call includes assessing current smoking status, identifying withdrawal symptoms and how the patient handles them, review of behavior modifications, assessment of reward planning, medication reconciliation, assessment for adherence, concerns, and adverse events with therapy, and education as needed on the above areas.

Patients will be scheduled to return to the Maternal Fetal Care Clinic 2-weeks after their quit date to obtain additional voucher to refill patches or bupropion. At each voucher pick-up, the patient will need to report her smoking status then perform an exhaled carbon monoxide level.

**Protocol Title:** Smoking Cessation Following Text Message Intervention in Pregnant Women

---

Patients will be continued to be seen on a bi-weekly schedule to obtain additional vouchers for patches or for bupropion, meet with the pharmacist, and complete a carbon monoxide exhalation test. These visits will be continued until the pharmacotherapy course is complete.

As the only intervention in this study is text messaging and the primary outcome measure is smoking cessation, we plan to continue the study through the patient's delivery. The patient may discontinue enrollment at any time.

Text Message Intervention  
Smoking Cessation Text Messages

\*Prior to quit date

\*Inform others:

Congratulations, your quit date is in 3 days! Let friends and family know you are planning to quit and how they can help support you. Support is one of the key pieces to quitting smoking!

\* Remove reminders:

Congratulations, your quit date is in 2 days! Get rid of things such as lighters, ashtrays, and cigarettes. Clean your car, house, and clothes so they don't smell like cigarette smoke when you quit.

\*Prepare for cravings:

Congratulations, your quit date is tomorrow! Remember that cravings will only last about 20 minutes, so have activities planned to distract yourself! Do a crossword puzzle, take a walk, clean the house, eat a healthy snack if you're hungry, etc.

\* Reasons why you're quitting

Congratulations, TODAY is your quit date! Look at the list of reasons you made for quitting and remind yourself of what a great thing you are doing for yourself and for baby! Start using your (patch) today now that you are ready to be smoke free. We are here to answer any questions (phone #)

\* During quit attempt

\*Mid-afternoon of quit date

Starting to have a craving? Go for a brief walk outside and breathe in some nice fresh air! You can do this!!

\* Day 2

Wow! You made it through day 1! Keep up the great work. Remember that cravings don't last more than 20 minutes, so do something fun or work on a project to distract yourself!

\* Day 3

Yeah! 3 smoke free days! Your carbon monoxide level in your blood has decreased to normal, which means your blood oxygen level has increased to normal. More oxygen for you and for baby!

\* Day 5

Have you noticed that your sense of taste and smell has improved? Keep up the great work! Remember that mixing up your routine during the times you used to smoke can help make it easier to stay smoke free!

\* Day 7

Congratulations! You have gone 1 week without smoking! Your body is already benefitting from quitting smoking, such as lower heart rate and blood pressure! Keep up the great work and contact your clinical pharmacists with any questions!

\* Day 10

You are doing great! Remember, if you have a slip up and smoke a few cigarettes, don't be discouraged! This doesn't mean you have failed and should keep smoking—just get back on

**Protocol Title:** Smoking Cessation Following Text Message Intervention in Pregnant Women

---

track right away! Think about what triggered it and how you will deal with it next time. We can help!

\* Day 14

Congratulations! You have gone almost 2 weeks without smoking! Don't forget to pick up your (patches, gum) from the office. You may notice that your lung function and circulation is starting to improve. If you are breathing easier, baby is getting more oxygen too!

\* Day 21

Congratulations! It has been 3 weeks since your quit date! Think about how much money you have saved on cigarettes so far and treat yourself to something special! You may notice less withdrawal symptoms and cravings as well. Keep up the good work!

\* Day 28

Congratulations! You have been smoke-free for almost 1 month! Don't forget to pick up your (patches) from the office.

Check-ins every 2 weeks thereafter

oSimilar reminders every 2 weeks until therapy is complete

Delivery

If available, delivery details will be abstracted from the patient charts and shall include gestational age at delivery, fetal weight, APGAR scores, and umbilical cord gases.

- c) **If the proposed study is a clinical trial where a drug, vaccine, device or other treatment is compared to a placebo group or comparison treatment group, what are the guidelines or endpoints by which early decisions regarding efficacy or lack of efficacy can be made? For example, it may be reasonable to stop enrollment on a study when efficacy has already been clearly demonstrated, to avoid unnecessary enrollments of additional subjects. Alternatively, it may be reasonable to stop enrollment when it is clear that efficacy will never be demonstrated, given the statistical power of the study as designed. Describe the guidelines that are in place to assist in making these determinations, if relevant to the proposed study.**

N/A

- d) **Describe how data analysis will be performed (statistical tests, methods of evaluating data) and indicate the smallest group/unit for which separate reporting will occur. For studies involving a questionnaire, if data and reliability information are available, please describe or provide references. For full board, unfunded studies describe sample size determination and power analysis. If none, please justify.**

Power Calculation

Based on previous experience, we anticipate 30% of patients will stop smoking at 2 weeks and anticipate texting will increase cessation rates by an additional 5%. Using G\*Power, based on a Chi square test, alpha of 0.05, power of 0.8, and medium effect size of 0.5, we estimate needing 52 patients. We anticipate 15% lost to follow-up or drop outs, so we anticipate needing 60 patients for this pilot project.

G\*Power is a free online statistical tool for calculating power in social, behavioral, and biomedical sciences.

Outcomes and Statistical Analysis

Primary Outcome- Smoking cessation rate verified by exhaled carbon monoxide levels (<8ppm) at 2weeks of quit date between texting and control group

Statistical Analysis- Chi-squared or Fischer's Exact Adjusted for confounders: multiregression

**Protocol Title:** Smoking Cessation Following Text Message Intervention in Pregnant Women

---

Statistical Analysis- Chi-squared or Fischer’s Exact Adjusted for confounders: multiregression analysis

Secondary Outcomes-Comparison between self-reported quit rates and verification through exhaled carbon monoxide levels  
Statistical Analysis- McNemar’s

Secondary Outcome-Change in exhaled carbon monoxide levels between baseline and 2 weeks  
Statistical Analysis-Paired t-test

Secondary Outcome-Comparison for demographics and verified cessation rates at 2 weeks  
Statistical Analysis-Parametric: t-tests, Nonparametric: Chi-squared or Fisher’s exact

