The primary objective of the study is to evaluate the impact of a text-message service on smoking cessation in medically underserved, obstetric patients when added to the usual care of pharmacist-driven CBT smoking cessation program and smoking cessation pharmacotherapy with either the nicotine replacement patch or bupropion. The smoking cessation rate will be verified by exhaled carbon monoxide levels (<8ppm) at 2 weeks of the patients quit date. Secondary objectives of the study include (1) a comparison of self-reported cessation versus verified cessation from the exhaled carbon monoxide level, (2) self-reported cessation rates at 1 month, 3 months, and delivery as verified by exhaled carbon monoxide levels, and (3) change in exhaled carbon monoxide levels from baseline to 2 week follow-up, (4), to better understand which patients may face additional barriers with tobacco cessation during pregnancy and ongoing use of marijuana and alcohol may be predictive.

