groups. We will use a random number generator to help with patient randomization. These numbers will be placed in a sealed envelope and shuffled. At the time of patient inclusion, an envelope will be selected by the pharmacist. However, if a patient declines receiving text messages but consents to participate in the pharmacist driven CBT and NRT, she will be enrolled in the standard of care group. A baseline carbon monoxide level will be obtained.

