#### Description of Usual Care

The patient, regardless of group, will have the standard of care smoking cessation visit with the clinical pharmacy specialist or PGY2 ambulatory care resident. The visit will include

- Medication reconciliation
- Review social history which includes use of street drugs and alcohol, allergies, and vaccine history
- Obtain smoking history that included current amount smoking, changes in smoking habits during this pregnancy, number of years smoked, quit attempt history, and use of previous smoking cessation aids
- Design a quit plan that includes setting a quit date within the next 30 days, obtain follow-up contact information, identify motivators/triggers/barriers, discuss withdrawal symptoms, develop plan for management of withdrawal symptoms, develop a plan for behavior modifications, discuss rewards, handling of relapse, medication options for cessation during pregnancy, and education on purpose, proper use, potential maternal and neonatal adverse events

If the pharmacist, physician, and patient deem that pharmacotherapy is appropriate, the patient will receive a 2 week supply if using NRT or 3 week supply if using bupropion. The smoking cessation pharmacotherapy will be supplied free of charge to the consenting participants. If the patient is prescribed NRT patches, the medication will be provided in two week intervals. If the patient is prescribed bupropion, the medication will be provided for a 3 week supply with the initial dispensing and 2 week supply thereafter. Dosing and length of treatment will follow package insert approved dosing. Patients will receive a voucher to take to the Clayton Health Services Pharmacy located across the street from the Maternal Fetal Care Clinic to receive either medication at no cost.

Demographics, social history, gestation age at enrollment, estimated due date, medications at enrollment, past medical history, and obstetric history include gravity and parity will be obtained from the EPIC medical record. Patients will be asked about smoking history, time to first morning cigarette, previous quit attempts, previous experience with cessation pharmacotherapy, motivators, triggers, and barriers during initial visit.

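### The primary analysis set and the rule for a missing 2-week carbon monoxide test are undefined, women who decline texts join the control group by choice, and no test is explicitly described for women without medication

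*Combined protocol and SAP*

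**What the plan says.** Section 2b sets the endpoint: "The smoking cessation rate will be verified by exhaled carbon monoxide levels (<8ppm) at 2 weeks of the patients quit date". Section 3d repeats it as the primary outcome, compared between arms by a chi-squared or Fisher's exact test with an adjusted regression.

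The follow-up part of section 3b, whose heading names both groups, describes how the test is done. "Patients will be scheduled to return to the Maternal Fetal Care Clinic 2-weeks after their quit date to obtain additional voucher" gives the visit and its purpose, and "At each voucher pick-up, the patient will need to report her smoking status then perform an exhaled carbon monoxide level" gives the occasion of the test. Later visits continue until the medication course ends. Under Description of Usual Care, medication is conditional: "If the pharmacist, physician, and patient deem that pharmacotherapy is appropriate, the patient will receive a 2 week supply" for patches, or three weeks' supply for bupropion.

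Contact differs by arm in one respect. Both arms are telephoned: "Usual follow-up includes a telephone call to the patient within 3 days of the quit date then weekly for 2 weeks afterwards". Under Intervention Group, the texting arm has more: "Patients will also receive text messages when they need to replenish their smoking cessation patches". Its day 14 message reminds the woman not to "forget to pick up your (patches, gum) from the office".

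On allocation, section 3b uses sealed envelopes but adds an exception: "if a patient declines receiving text messages but consents to participate in the pharmacist driven CBT and NRT, she will be enrolled" in the standard-of-care group. Section 3d allows for 15% loss when setting the sample size. It does not say who is analysed or what happens to a woman with no 2-week reading.

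**The concern.** Three gaps meet at the primary endpoint.

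- **Testing route.** The test is described at voucher pick-up, and a woman without medication has no voucher to pick up. It is also unclear whether a woman with a three-week first supply of bupropion needs one at 2 weeks, because the start of treatment relative to the quit date is not stated.
- **Who is compared.** Women who refuse texts are placed in control by preference, and nothing says whether they count in the primary comparison. If they do, the control arm is no longer a purely randomised group.
- **Missing tests.** With no rule fixed in advance, the choice between counting missing as smoking and analysing attenders only can be made after the data are seen. That choice can change the size and even the sign of a spurious difference.

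The day 14 text bears on the third gap. It reaches one arm only, at the primary time point, and points to the place where the test is done. If it changes attendance, the comparison mixes help with quitting and help with turning up.

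**Working it through.** **Inputs from the plan.** Section 3d gives 30% cessation at 2 weeks, 5 points more with texting, 15% loss, and 52 women raised to 60. The last step reproduces: 52 × 1.15 = 59.8, so 60. (Whether 52 is itself right is a separate question.) Sections 8b and 8c give 100 women. At 15% loss, 0.15 × 60 = 9 or 0.15 × 100 = 15 women have no result. The plan gives no attendance by arm, no share without medication and no share declining texts, so those values below are assumptions.

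**Formulas.** Let q be the true quit rate, and aQ and aS the attendance of quitters and of smokers.

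- Missing counted as smoking: observed rate = q·aQ.
- Attenders only: observed rate = q·aQ / (q·aQ + (1 − q)·aS).

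**No true effect (q = 0.30 in both arms), overall attendance 90% texting and 80% control (15% loss overall).**

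| Who is missing | Missing = smoking | Attenders only |
|---|---|---|
| Attendance unrelated to quitting | 0.30×0.90 − 0.30×0.80 = +3.0 points | 0.30 − 0.30 = 0 |
| Only smokers are missing | 0.30 − 0.30 = 0 | 0.30/0.90 − 0.30/0.80 = −4.2 points |

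The same attendance gap gives +3.0, 0 or −4.2 points, depending on the rule and on who stays away. If attendance is 85% in both arms with the same pattern, every cell is 0. Under missing = smoking, with attendance unrelated to quitting, a gap of 0.05/0.30 = 16.7 points would by itself produce the planned 5-point difference.

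**True effect as planned (35% against 30%), missing = smoking, attendance unrelated to quitting.**

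| Attendance, texting / control | Observed difference | Against the true 5.0 |
|---|---|---|
| 85% / 85% | 0.2975 − 0.2550 = 4.25 points | understated |
| 86% / 85% | 0.3010 − 0.2550 = 4.6 points | understated |
| 90% / 80% | 0.3150 − 0.2400 = 7.5 points | overstated |

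**Sampling error.** The 95% half-width is 1.96·√(2 × 0.3 × 0.7 / n). It is 0.232 at n = 30 per arm (60 women) and 0.180 at n = 50 per arm (100 women).

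**Decliners.** Suppose 5%, 10% or 20% of 60 women decline and the rest split equally.

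| Decliners | Randomised per arm | Decliners' share of the control group | Half-width without decliners |
|---|---|---|---|
| 3 | 28.5 | 3/31.5 = 10% | 0.238 |
| 6 | 27 | 6/33 = 18% | 0.244 |
| 12 | 24 | 12/36 = 33% | 0.259 |

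Including them shifts the control quit rate by that share of whatever difference exists between decliners and randomised controls. The documents do not allow that difference to be estimated.

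**The case against.** The 2-week return is scheduled for patients in both groups, and section 8h requires willingness to keep the visit schedule. Section 2b describes usual care as including medication, section 9.7 says the control group is provided with patches or bupropion, and section 2b also plans CO verification at 1 month, 3 months and delivery. Testing was therefore probably not meant to depend on a voucher. This stands: the testing gap is one of wording, and the number of women affected is unknown and may be small. A reader might infer that unmedicated women are excluded or go untested; the documents do not say so.

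A reader might also infer that the day 14 text biases the trial toward texting. That is not supported. The text concerns medication, not the CO test, and goes out for a visit already scheduled in both arms. Control women have the same free medication to collect, and both arms are telephoned. A visit reminder is not among the listed call contents, but the phone script, refill text script, data collection sheet and grant proposal are attachments that were not available, so a reminder or rule there cannot be ruled out.

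Nor does counting missing as smoking always favour texting when texts raise attendance. That holds against the truth only when texting has no effect. At 35% against 30%, attendance of 86% and 85% understates the benefit.

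Finally, item 8c of the expedited review page, marked on this form, covers research with only data analysis remaining. Changes to visits may therefore come too late. That limits the remedy but leaves the gap in section 3d open.

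**Conclusion.** The point holds in a limited form and should be fixed. As written, the primary comparison can include women who chose the control group, and it can depend on a missing-data rule selected later. These are the firm parts. The absence of an explicit 2-week test for unmedicated women is a real omission of unknown, possibly small, reach. Unequal attendance caused by the texting-only prompt is possible, not shown.

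On size, a 10-point attendance gap with no true effect yields at most about 3 points in favour of texting, or about 4 against, in the two patterns worked above. This is comparable with the planned 5-point effect but well below the half-width of about 23 points at 30 per arm. All of these figures rest on assumed attendance and illustrate the mechanism; they do not estimate what happened. Confidence is medium, because the unseen attachments could close part of the gap.

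**What to change.** 1. **Section 3d, in any case.** Make the primary analysis all randomised women in their allocated arm, with a missing 2-week CO test counted as not verified quit. Exclude women assigned to control only because they declined texts before randomisation, and report them separately. Keep a woman who declines after allocation to texting in the texting arm. Report 2-week attendance by arm. Add an attenders-only analysis and sensitivity analyses that let missingness favour either arm, and note that counting missing as smoking can over- or understate a true effect.
2. **Section 3b, if visits are still under way.** State that smoking status and CO are obtained from every enrolled woman at the scheduled 2-week visit, whether or not she needs a voucher. Give the same visit reminder to both arms in the calls already planned. Leave the refill texts unchanged, since they are part of the intervention under test.
3. **If only data analysis remains.** Apply item 1 and date it, label it post hoc if the arms have already been compared, and report the texting-only office prompt as a limitation.

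The cost is a few lines in 3d and, if still relevant, one sentence in 3b and one line in the phone script. The phone script is an approved attachment, so changing it needs IRB approval. Call days are not fixed, so the reminder may come some days before the visit. Excluding decliners widens the half-width from about 23 points to 24–26 if 5–20% of 60 women decline (assumed).

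### Secondary objective 2 promises carbon-monoxide-verified cessation at 3 months and delivery, but the procedures shown define no self-report or breath test at either point for any woman

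*Combined protocol and SAP*

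**What the plan says.** All references are to the Combined protocol and SAP.

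- **Objective (section 2b).** Secondary objective 2 is "self-reported cessation rates at 1 month, 3 months, and delivery as verified by exhaled carbon monoxide levels".
- **Visits (section 3b, Follow-up phone calls and visits).** "Patients will be scheduled to return to the Maternal Fetal Care Clinic 2-weeks after their quit date to obtain additional voucher". The measurement rule is "At each voucher pick-up, the patient will need to report her smoking status then perform an exhaled carbon monoxide level". Two-weekly visits follow, at which women collect vouchers, see the pharmacist and "complete a carbon monoxide exhalation test". The stopping rule is "These visits will be continued until the pharmacotherapy course is complete", and the lay summary in section 2a repeats it.
- **Drug course (section 3b, Description of Usual Care).** Medication is conditional: "If the pharmacist, physician, and patient deem that pharmacotherapy is appropriate". Its duration is left to an outside source: "Dosing and length of treatment will follow package insert approved dosing".
- **Phone calls (same follow-up section).** One call is made within 3 days of the quit date, then weekly calls for 2 weeks. They ask about smoking status but involve no breath test.
- **Delivery (end of section 3b).** Where records exist, the plan is that "delivery details will be abstracted from the patient charts and shall include gestational age at delivery, fetal weight, APGAR scores, and umbilical cord gases". Section 11c adds that delivery follow-up is obtained by linking to the medical record.
- **Duration.** The follow-up section says the study will run until each patient delivers. It attaches no visit, call or test to that statement.
- **Analysis (section 3d).** No analysis is listed for cessation rates at 1 month, 3 months or delivery.

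**The concern.** The objective names three late time points and a method of verification, but the procedures supply neither self-report nor CO at two of them. This is more than missing detail, because the plan states a rule that ends measurement, and the rule follows medication use.

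Two things are at stake. First, delivery is the plan's only measure of abstinence lasting to the end of pregnancy, and the documents shown do not provide for it. Second, any late CO values that do exist would come from women still collecting medication. That group forms after randomisation and may form differently in an open-label trial where one arm also receives refill reminders by text. A comparison of arms within it is no longer a randomised comparison.

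The primary outcome at 2 weeks has its own scheduled visit and is not part of this point.

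**Working it through.** The plan gives no figure to reproduce here. The check sets the schedule against the objective, then shows how coverage varies with the one quantity the documents leave out, the course length.

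**Step 1. Last scheduled contact of each kind.**
- Phone: day 3 + 14 days = day 17 at the latest, self-report only.
- Clinic visit with self-report and CO: weeks 2, 4, 6 and so on, up to the end of the course.
- Delivery: chart abstraction, with no smoking item listed.

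The 1-month point is covered for a woman whose course lasts at least 4 weeks. No assessment is defined at 3 months or at delivery. A woman given no medication has no voucher series at all.

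**Step 2. Incidental coverage.** Let D be the course length in weeks from the quit date. D is an assumption, taken over 6 to 26 weeks. Three months is 13 weeks. A woman is still on course at delivery if gestation at quit date + D is at least gestation at delivery, G. Assume quit dates spread evenly from L weeks (L = 6, 12 or 20) up to the 35-week limit in the inclusion criteria. For G − D at or above L, the share still on course is

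(35 − (G − D)) / (35 − L),

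and it is 100% where G − D is below L. For example, with D = 12 and G = 40, G − D = 28. The share is 7/29 = 24% for L = 6, 7/23 = 30% for L = 12, and 7/15 = 47% for L = 20.

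| D (weeks) | Last visit short of week 13 by | On course at delivery, G = 40 | On course at delivery, G = 37 |
|---|---|---|---|
| 6 | 7 weeks | 3–7% | 14–27% |
| 8 | 5 weeks | 10–20% | 21–40% |
| 10 | 3 weeks | 17–33% | 28–53% |
| 12 | 1 week | 24–47% | 34–67% |
| 14 | reaches it | 31–60% | 41–80% |
| 20 | reaches it | 52–100% | 62–100% |

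These shares are upper bounds, since they suppose that every woman takes medication and completes the course. Even then the value is the nearest two-weekly visit, not a delivery assessment.

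**Step 3. One woman as illustration.** Quit date at 20 weeks and delivery at 39 weeks leave 19 weeks. With D = 8 to 12, the last CO test is 19 − 12 = 7 to 19 − 8 = 11 weeks before delivery, and 13 − 12 = 1 to 13 − 8 = 5 weeks before the 3-month point.

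**Step 4. Calendar (sections 2c and 8k).** Enrolment stops at the end of April 2015 and data collection closes on 1 June 2015, 32 days later. A quit date after about 1 March 2015 cannot reach 3 months before the close. A woman at 20 weeks needs 20 more weeks to reach 40, so a quit date after about 12 January 2015 cannot reach delivery at 40 weeks.

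**The case against.** The strongest reply has four parts.

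- **The plan intends follow-up to delivery and says so.** That is right, and it shows that delivery outcomes were wanted. It gives a duration, however, and names no assessment, so it sharpens the inconsistency without resolving it.
- **The documents shown are incomplete.** The data collection sheets, the phone script and the grant proposal are listed in section 16 but not shown, and the list of delivery items need not be exhaustive. This stands. A reader might infer that the trial cannot report verified cessation at delivery. The documents do not support that, because a late assessment may sit in an attachment. The point is limited to the procedures as shown.
- **Course length is unknown.** A reader might infer that most women lack late measurement. The documents do not establish this. With a 12-week course the week-12 visit could reasonably serve as the 3-month visit, since no window is defined. With delivery at 37 weeks up to 67% could still be on course. The 3-month gap may therefore be small, and the delivery gap is the firmer one.
- **The direction of bias is not shown.** A reader might infer that late figures would overstate cessation. Women who quit easily may stop medication early, and those still collecting it may be struggling. Selection after randomisation is a fair concern, but its sign is unknown.

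The late time points are also secondary outcomes in a self-described pilot, which limits the weight of the point.

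**Conclusion.** The concern holds for the procedures as shown. Objective 2 asks for verified cessation at 3 months and delivery, and no self-report or CO test is defined at either point for any woman. Any coverage is a by-product of an optional drug course of unstated length.

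The size is conditional. For courses of 6 to 10 weeks, no scheduled visit falls within 3 weeks of the 3-month point except at exactly 10 weeks. At 12 weeks the shortfall is one week. For delivery at 40 weeks, at most 3 to 7% of women (6-week course) to 24 to 47% (12-week course) would still be attending. These ranges rest on assumed course lengths, evenly spread quit dates and full adherence. The absence of a defined assessment rests on none of them.

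This should be corrected, but it does not touch the 2-week primary comparison.

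**What to change.** Reconcile sections 2a, 2b and 3b (follow-up visits and delivery) so that the objective and the schedule agree. Which route applies depends on whether follow-up is still open. The Expedited Paragraphs section marks item 8(c), meaning that only data analysis remains, which points to the second route.

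**If follow-up is open.** Separate outcome assessment from the drug course. Record self-report and then CO in every randomised woman, whatever her medication, at the routine prenatal visits nearest 1 and 3 months after the quit date and at the last prenatal visit. For a quit date after 40 − 13 = 27 weeks, 3 months falls after a 40-week delivery, so state that the last prenatal visit is then the final assessment. Align the 1 June 2015 data collection date in sections 2c and 8k with these points, since late enrollees cannot otherwise reach them. Add the matching analysis to section 3d. The cost is up to three short breath tests per woman, plus longer follow-up for late enrollees if the closing date moves.

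**If follow-up is closed.** Restate objective 2 so that verified cessation is claimed only for time points with a CO visit, and remove the CO qualifier for 3 months and delivery. Report the number measured in each arm at each time point. Describe any late values as coming from women still attending. This costs a wording change and a table of counts, with no new data.

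Neither route changes clinical management.
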